## Schema

Post-menopausal patients with histologically confirmed  
stage I-III, ER+/HER2- breast cancer  
(excess tissue must be available from diagnostic biopsy specimen)

Enroll first

Arm A  
no drug treatment

Enroll second

Arm B  
Letrozole (2.5 mg/day)  
for 10-21 days

Surgical resection of primary tumor

Fresh tumor specimen promptly taken to Pathology for dissection

Tissue requirements for study (1-mm punch cores):  
≥4 fresh, viable cores in tissue culture medium  
2 cores snap-frozen in liquid nitrogen  
2 cores formalin-fixed, paraffin-embedded

End of study

**ABBREVIATIONS**

CPHS	Committee for the Protection of Human Subjects at Dartmouth College
DMBA	7,12-Dimethylbenz(a)anthracene
DSMAC	Data Safety Monitoring and Accrual Committee of the Norris Cotton Cancer Center
ER	estrogen receptor alpha
FDA	Food & Drug Administration (U.S.)
FFPE	formalin-fixed, paraffin-embedded
HER2	HER2 / ERBB2 proto-oncogene
IGF-1R	insulin-like growth factor receptor
IHC	immunohistochemistry
InsR	insulin receptor
IRS1	insulin receptor substrate 1
IRS2	insulin receptor substrate 2
mRNA	messenger RNA
mTOR	mammalian target of rapamycin
mTORC1	mTOR complex 1
mTORC2	mTOR complex 2
PHI	protected health information
PI	primary investigator
PI3K	phosphatidylinositol 3-kinase
PR	progesterone receptor
OPRR	Dept. of Health and Human Services Office for Protection from Research Risks (U.S.)

## 1.0 INTRODUCTION

### 1.1. Breast cancer

Most patients are diagnosed with Stage I-III breast cancer, which is localized to the breast (and adjacent lymph nodes), and is surgically resectable and potentially curable. Seventy-five percent of primary breast tumors express estrogen receptor alpha (ER). Patients with Stage I-III ER-positive breast cancer are typically treated with adjuvant anti-estrogen therapy for 5 years after surgical removal of the primary tumor. Among the cases of ER+ breast cancer, ~10% harbor genomic amplification of the *ERBB2* (HER2) proto-oncogene; patients with HER2+ cancer are treated with HER2-directed therapy, and will not be part of this study. This study focuses on patients with Stage I-III ER+/HER2- breast cancer.

### 1.2. The presurgical study model

An initial diagnosis of breast cancer is typically made by histological confirmation of a tissue biopsy specimen. Patients with Stage I-III cancer will then typically undergo surgery within a few weeks to remove the primary tumor(s). Therefore, it is common to have a paired tumor biopsy specimen and a surgical tumor specimen. The availability of such paired specimens has prompted a large initiative in recent years to treat patients (e.g., with drug) during the intervening period between the time of diagnostic biopsy and the time of surgery. We can then compare the biopsy tissue (baseline, pre-treatment) to the surgical tissue (post-treatment) to assess biological changes (e.g., changes in mRNA and protein expression). This study design has provided a wealth of information on the effects of systemic therapies on tumor biology [reviewed in ref. (1)], and it requires no additional biopsy procedure.

### 1.3. Therapeutic inhibition of mTORC1

mTORC1 is a molecular hub that integrates signaling inputs from an array of sources, including growth factor receptor signaling pathways, nutrient sensing pathways, and energy sensing pathways. Activated mTORC1 promotes cap-dependent protein translation, and this pathway is hyperactivated in many cancer types. As such, mTORC1 is an attractive therapeutic target. The mTORC1 inhibitor RAD001 (Afinitor, Everolimus) was recently approved for the treatment of patients with advanced/metastatic ER+/HER2- breast cancer in combination with the steroidal aromatase inhibitor Exemestane following progression on a non-steroidal aromatase inhibitor (Letrozole, Anastrozole). Everolimus is also approved for the treatment of other non-breast malignancies. While the phase 3 BOLERO-2 study demonstrated that Exemestane/Everolimus increased progression-free survival compared to Exemestane/Placebo (2), nearly all patients eventually progressed. Genetic analysis has not identified a clear, individual biomarker that predicted benefit from Everolimus (3). Furthermore, it is unclear

whether continued treatment with Exemestane (in the context of Everolimus) is beneficial, given that the 3 major aromatase inhibitors in clinical use have been shown to be equally efficacious on a population level (4, 5); this issue is being addressed in the ongoing BOLERO-6 study (NCT01783444; testing Everolimus vs. Exemestane/Everolimus vs. Capecitabine; same patient population as in BOLERO-2).

In some cell types, including ER+ breast cancer, mTORC1-induced activation of p70-S6-kinase (p70S6K) elicits negative feedback whereby p70S6K phosphorylates the insulin-like growth factor-1 receptor (IGF-1R)/ insulin receptor (InsR) effector IRS-1 to promote IRS-1 degradation (Fig. 1). Thus, mTORC1 inhibition (with RAD001) blocks this negative feedback, inducing upregulation of IGF-1R/InsR/IRS-1/2 signaling that in turn activates PI3K/AKT and MEK/Erk to promote cell survival (6-9). As such, mTORC1 inhibitors may stimulate cancer cell survival pathways. Circumventing these effects of mTORC1 inhibitors may increase therapeutic efficacy.

[figure not shown]

Fig. 1. mTORC1 inhibition blocks negative feedback signaling from p70S6K to IRS-1/2. This promotes IRS-1/2 activation, which in turn promotes PI3K/AKT activation and cell survival. The genes encoding IRS1, IRS2, and IGF-1R are transcriptionally activated by ER. Hence, anti-estrogen-mediated suppression of IGF-1R, IRS1, and/or IRS2 expression blunts activation of PI3K/AKT induced by mTORC1 inhibition.

#### 1.4. Preclinical findings

We observed that mTORC1 inhibition with RAD001 in ER+ breast cancer cell lines induces upregulation of PI3K/AKT signaling (Fig. 2). Pretreatment with the anti-estrogen fulvestrant (which blocks ER transcriptional activity) suppressed RAD001 -induced PI3K/AKT signaling. *IGF1R*, *IRS1*, and *IRS2* are ER-induced genes, and studies have demonstrated crosstalk between the ER and IGF-1R pathways at several levels [reviewed in (10)]. Fulvestrant treatment decreased the levels of IGF-1R, IRS-1, and IRS-2 at the protein and/or mRNA levels, which likely suppressed RAD001-induced PI3K/AKT activation. These findings suggest that continued anti-estrogen therapy would be beneficial in the context of treatment with RAD001 in patients.

Presurgical treatment with the aromatase inhibitor Letrozole for 3 days is sufficient to significantly suppress plasma estrogen levels. Gene expression profiling of pre-treatment (baseline, diagnostic biopsy) and post-two-week-treatment (surgical) ER+ tumor specimens revealed that estrogen deprivation via Letrozole induced changes in expression of ER-regulated genes. *IRS1* was one of the most significantly and consistently downregulated genes when comparing pre- and post-treatment samples. *IGF1R* was also significantly downregulated by Letrozole (11).

[figure not shown]

Fig. 2. Anti-estrogen-mediated inhibition of ER with fulvestrant abrogates PI3K/AKT activation induced by mTORC1 inhibition with RAD001. *Left:* MCF-7 cells were pre-treated with medium containing 10% FBS  $\pm$  1  $\mu$ M fulvestrant for 24 hours. Then cells were treated with medium  $\pm$  1  $\mu$ M fulvestrant  $\pm$  20 nM RAD001 for 24 hours before lysis. Lysates were analyzed by immunoblotting using the indicated antibodies. *Right:* ZR75-1 cells were pre-treated with medium containing 10% FBS  $\pm$  1  $\mu$ M fulvestrant for 3 days. Then cells were treated with medium  $\pm$  1  $\mu$ M fulvestrant  $\pm$  20 nM RAD001 for 24 hours before lysis. Lysates were analyzed as in (A). Note that RAD001 treatment decreases P-S6 (marker of mTORC1 activity) but increases P-AKT. Fulvestrant treatment decreases IRS-1 and IGF-1R levels, which are encoded by ER-inducible genes.

### 1.5. Presurgical endocrine therapy

Letrozole is appropriate neoadjuvant therapy for postmenopausal women with hormone receptor positive breast cancer. Ellis et al randomized 250 post-menopausal women with locally-advanced hormone receptor positive breast cancer requiring mastectomy, to four months of neoadjuvant endocrine therapy with either letrozole or tamoxifen. Sixty percent of subjects receiving presurgical letrozole had an objective radiologic response and 48% were able to undergo breast-conserving surgery, while only 41% of subjects receiving tamoxifen had an objective response and 36% were able to undergo breast-conserving surgery (12). The Ki-67 proliferation biomarker can be assayed at diagnosis and again after a short run-in period of treatment with letrozole, and Ellis showed that suppression of Ki-67 with persistent expression of ER in a node negative patient with a primary tumor under 5 cm in size is predictive of such a low risk of recurrence that adjuvant chemotherapy is obviated (13). 377 post-menopausal women with clinical Stage II-III hormone receptor positive breast cancer were randomized to receive letrozole, anastrozole, or exemestane for 16 to 18 weeks prior to surgery. The clinical response rate to letrozole was 75% versus 69% for anastrozole and 63% for exemestane. 51% of the patients who were judged to require a mastectomy at the time of study registration were able to achieve breast preservation (14). Neoadjuvant endocrine therapy can therefore increase the likelihood of achieving breast preservation in a woman with a locally advanced hormone receptor positive breast cancer, and biopsies after a brief treatment interval have provided biomarkers which were predictive of prolonged disease-free survival with endocrine therapy alone. Letrozole is an active agent in the neoadjuvant setting and can be considered an appropriate standard of care as neoadjuvant therapy for locally advanced breast cancer.

### 1.6. Study rationale

We propose a presurgical study in patients with Stage I-III ER+/HER2- breast cancer to determine whether anti-estrogen therapy (Letrozole) suppresses mTORC1 inhibitor (RAD001)-induced activation of PI3K/AKT signaling. As the primary objective is to determine whether anti-estrogen therapy alters mTORC1 inhibitor-induced signaling that can be assessed in a short time frame *ex vivo*, we will treat patients with or without Letrozole for 10-21 days prior to surgery; this time frame will allow sufficient time for maximal estrogen suppression and downstream changes in the levels of ER-regulated transcripts and encoded

proteins. Viable core samples of surgically resected tumors will be used for *ex vivo* culture to assess the effects of RAD001 on signaling, to avoid exposing subjects to potentially adverse side effects of RAD001. Findings from this study will provide mechanistic insight into the effects of mTORC1 and ER inhibition on oncogenic signaling pathways in cancer cells.

## 2.0 OBJECTIVES

### 2.1 Primary Objectives

1. Arm A: To determine whether mTORC1 inhibition with RAD001 increases IRS-1/PI3K/AKT pathway activation in ER+/HER2- breast tumors *ex vivo*.
2. Arm B (comparison with Arm A): To determine whether presurgical treatment of patients with ER+/HER2- breast cancer with Letrozole suppresses IRS-1/PI3K/AKT pathway activation compared to tumors from untreated patients.

### 2.2 Secondary objectives

1. To determine whether presurgical treatment with Letrozole suppresses IRS-1/PI3K/AKT pathway activation compared to baseline.
2. To determine whether the level of IRS-1/PI3K/AKT pathway activation is correlated with rate of tumor cell proliferation as determined by Ki67 score.
3. To determine whether RAD001-induced changes in IRS-1/PI3K/AKT signaling *ex vivo* are correlated with rate of tumor cell proliferation as determined by Ki67 score.
4. To identify changes in mRNA levels of ER-regulated gene induced by presurgical treatment with Letrozole.

## 3.0 ELIGIBILITY CRITERIA

### **Inclusion Criteria:**

- 3.1. Histologic documentation of invasive breast cancer by core needle or incisional biopsy. Excess baseline biopsy tumor tissue sufficient to make three 5-micron sections must be available for molecular analyses as part of this study.
- 3.2. The invasive cancer must be estrogen receptor alpha (ER)-positive, with ER staining present in greater than 50% of invasive cancer cells by IHC
- 3.3. The invasive cancer must be HER2-negative (IHC 0-1+, or with a FISH ratio of <1.8 if IHC is 2+ or if IHC has not been done).
- 3.4. Clinical Stage I-III invasive breast cancer with the intent to treat with surgical resection of the primary tumor. Tumor must be  $\geq 2$  cm to provide adequate tissue.

- 3.5 Patients with multicentric or bilateral disease are eligible if the target lesions meet the other eligibility criteria. Samples from all available tumors are requested for research purposes.
- 3.6. Women  $\geq$  age 18, for whom adjuvant treatment with an aromatase inhibitor would be clinically indicated. Women must be either post-menopausal, or pre-menopausal having undergone oophorectomy.
- 3.7. Patients must meet the following clinical laboratory criteria:
  - Absolute neutrophil count (ANC)  $\geq$  1,000/mm^3 and platelet count  $\geq$  75,000/mm^3.
  - Total bilirubin  $\leq$  1.5  $\times$  the upper limit of the normal range (ULN).
  - Alanine aminotransferase (ALT) and aspartate aminotransferase (AST)  $\leq$  3  $\times$  ULN.
- 3.8. Ability to give informed consent.

**Exclusion Criteria:**

- 3.8. Prior endocrine therapy for any histologically-confirmed cancer is not allowed. Prior endocrine therapy that was administered  $\geq$  5 years ago for the prevention of breast cancer in patients with no history of breast cancer is allowed.
- 3.9. Systemic drug treatment to induce ovarian suppression if woman is pre-menopausal.
- 3.10. Any other neoadjuvant therapy for breast cancer [*i.e.*, treatment with any other anti-cancer agent besides Letrozole (10-21 days) before surgical resection of the primary breast tumor].

**4.0 REGISTRATION**

Patients will be registered by the Clinical Research Associate through the Norris Cotton Cancer Center Clinical Trials office following completion of pre-treatment evaluations and informed consent. At the time of registration, the following information will be recorded:

- Patient's name and subject identification number.
- Patient's date of birth.
- Date of treatment start.

Eligibility criteria will be verified at the time of registration. A case number will be assigned following registration.

## 5.0 TREATMENT PLAN

### 5.1 Screening Period

Subjects will provide written informed consent, be evaluated for eligibility criteria, and undergo standard baseline clinical and tumor assessments and staging. Subjects will undergo our standard pre-treatment surgical evaluation. To determine our ability to provide breast conservation, patients at DHMC have imaging of the breast prior to neoadjuvant chemotherapy to include mammography, ultrasound, and breast MRI, to determine the suitability of breast conservation, and to guide the surgical oncologist on surgical planning. This period will be up to 4 weeks prior to the start of presurgical treatment with Letrozole for subjects enrolled onto Arm B (this time period does not apply to Arm A).

### 5.2 Treatment Period

Patients will receive either A) no presurgical drug treatment, or B) presurgical treatment with Letrozole for 10-21 days prior to surgery. Arm A will enroll patients first until accrual is full (n=10). Following successful completion of molecular analyses to support the first primary objective (To determine whether mTORC1 inhibition with RAD001 increases IRS-1/PI3K/AKT pathway activation in ER+/HER2- breast tumors *ex vivo*), we will proceed to enroll patients in Arm B (presurgical Letrozole, as below in Section 5.2.2). An estimated 10 subjects will be enrolled into Arm B to obtain the necessary evaluable number of subjects (n=10).

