### 5.4. Evaluable patients

Subjects who proceed to a definitive surgical procedure with A) tumor tissue sufficient to provide punch biopsy specimens for research purposes, and B) histologically-confirmed tumor tissue in the surgical specimen with  $\geq 50\%$  tumor cellularity, will be considered evaluable. Subjects whose surgical specimens do not contain adequate tumor tissue to assess the primary endpoint will not be considered evaluable, and will need to be replaced.

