## 9.0 STATISTICAL CONSIDERATIONS

9.1 PRIMARY ENDPOINT – The primary endpoint of this trial is the level of IRS-1/PI3K/AKT pathway activation in primary tumors, measured by densitometric analysis of immunoblot signals of markers of pathway activation (IRS-1, phospho-IRS-1-Ser636/639, phospho-AKT-T308, phospho-AKT-S473).

9.2 SECONDARY ENDPOINT – The secondary endpoint is Ki67 score, as determined by the percentage of Ki67+ tumor cells by IHC.

9.3 PRIMARY ANALYSIS PLAN - The primary analyses determine whether RAD001 treatment of tumor samples *ex vivo*, and/or presurgical treatment of patients with Letrozole, alter IRS-1/PI3K/AKT pathway activation in breast tumors. Signal values of IRS-1, phospho-IRS-1-Ser636/639, phospho-AKT-T308, phospho-AKT-S473 will be determined by densitometric analysis of immunoblots. Below is an illustration of projected data and relevant comparisons. Signal values of control (DMSO)-treated and RAD001-treated tumor samples will be compared using a 2-sided paired t-test. These tests will be performed separately in tumors from each arm of the study (*i.e.*, untreated, or letrozole-treated, as shown below in *left* and *center* panels). An additional test will compare the magnitude of change in signal values in Arm A vs. Arm B (2-sided independent t-test), to determine whether Letrozole treatment alters response to RAD001 (shown below in *right* panel).

9.4 SECONDARY ANALYSIS PLAN – Secondary analysis to determine whether presurgical treatment with Letrozole suppresses IRS-1/PI3K/AKT activation compared to baseline will be achieved using a paired t-test comparing IRS-1/PI3K/AKT pathway markers scored by IHC analysis of matching tumor samples from patients acquired A) at baseline (diagnostic biopsy) and B) at surgery (post-Letrozole). We will also determine whether tumor Ki67 IHC score is associated with the level of IRS-1/PI3K/AKT pathway activation, or with RAD001-induced changes in IRS-1/PI3K/AKT signaling, by Spearman correlation between Ki67 score and densitometric signal values of pathway markers as determined by immunoblot analysis or IHC Histoscore.

9.5 STATISTICAL TESTING - All statistical tests will be 2-sided, and the overall type I error will be 0.05.

9.6 SAMPLE SIZE – The primary analyses determine whether RAD001 treatment of tumor samples *ex vivo*, and/or presurgical treatment of patients with Letrozole,

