alter IRS-1/PI3K/AKT pathway activation in breast tumors. RAD001-induced pathway activation will be defined as a  $\geq 50\%$  increase in phospho-AKT densitometric signal value compared to DMSO-treated control; this scoring system provides a binary metric for sample size determination for Arm B (below). Given that this is a pilot study, we do not know what fraction of ER+/HER2-breast tumors will exhibit RAD001-induced IRS-1/PI3K/AKT activation. Hence, tumors from 10 untreated patients in Arm A will be used to determine the frequency with which RAD001 induces AKT activation.

The fraction of tumors in Arm A (untreated patients) that exhibit RAD001-induced AKT activation will be used to determine the number of patients that need to be enrolled in Arm B (presurgical Letrozole treatment) to detect a significant effect of presurgical Letrozole treatment on RAD001-induced AKT activation. We estimate that  $\leq 15\%$  of Letrozole-treated tumors will exhibit RAD001-induced AKT activation. If we observe that RAD001 increases phospho-AKT in X of 10 tumors in Arm A, we will enroll Y patients in Arm B (presurgical Letrozole) to provide a sufficient number of tumors to detect a significant effect ( $p \leq 0.05$ ) of presurgical Letrozole on RAD001-induced changes in phospho-AKT levels with 80% power (calculated using uncorrected chi-squared statistic). If we observe that  $\leq 3$  tumors from untreated patients in Arm A exhibit RAD001-induced AKT activation, the study will be terminated at this point, and Arm B will not enroll patients. To account for interpatient/intertumor variability, we will enroll a minimum of 10 patients in Arm B.

X (n of tumors from untreated patients that exhibit a <math>\geq 50\%</math> increase in P-AKT levels in response to RAD001 treatment ex vivo)	Y (n of patients to be enrolled in Arm B, presurgical Letrozole)
0-3	Terminate study
4-6	30
7-8	14
9-10	10

- 10.

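### Section 5.2 fixes Arm B at 10 evaluable patients, but Section 9.6 requires 30, 14 or 10 depending on the Arm A result, and neither is given precedence

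*Combined protocol and SAP*

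**What the plan says.** Section 5.2 (Treatment Period) sets the accrual sequence. Arm A comes first: "Arm A will enroll patients first until accrual is full (n=10"). Arm B opens once the molecular analyses for the first primary objective have been completed successfully, and its size is then given: "An estimated 10 subjects will be enrolled into Arm B to obtain the necessary evaluable number of subjects (n=10"). The sentence does not depend on the Arm A result and does not refer to Section 9.6.

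Section 9.6 (Sample Size) makes Arm B depend on Arm A. The fraction of Arm A tumours with RAD001-induced AKT activation "will be used to determine the number of patients that need to be enrolled in Arm B". Activation means a rise of at least 50% in phospho-AKT signal over the DMSO control, and "this scoring system provides a binary metric for sample size determination for Arm B". With X activated tumours out of 10, the table gives:

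| X | Arm B patients, Y |
|---|---|
| 0-3 | study terminated |
| 4-6 | 30 |
| 7-8 | 14 |
| 9-10 | 10 |

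The number 10 also appears as a floor: "we will enroll a minimum of 10 patients in Arm B". The purpose of Y is "to provide a sufficient number of tumors to detect a significant effect" of Letrozole with 80% power. Under Section 5.4, subjects without adequate tumour tissue "will not be considered evaluable, and will need to be replaced".

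**The concern.** The two sections give different targets for the same arm. Section 5.2 is the operational section, so staff working from it would close Arm B at 10. Staff working from Section 9.6 might need 14 or 30. The schema gives no arm sizes, and no text settles precedence.

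Arm B serves the second primary objective in Section 2.1, the comparison of Letrozole-treated with untreated tumours. Its size is settled after the Arm A data have been seen. With two written targets, either number could then be chosen with support from the protocol. Section 5.2 also opens Arm B without mentioning the termination rule for X=0-3.

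**Working it through.** **1. The two targets side by side**

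| X | Section 5.2 | Section 9.6 | Shortfall under Section 5.2 |
|---|---|---|---|
| 4-6 | 10 | 30 | 20 of 30 (67%) |
| 7-8 | 10 | 14 | 4 of 14 (29%) |
| 9-10 | 10 | 10 | none |

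This step needs no assumptions and establishes the contradiction by itself.

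**2. Inputs for the power check**

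- Arm A size n_A = 10 (Sections 5.2 and 9.6).
- Arm A activation rate p_A = X/10 (Section 9.6).
- Arm B activation rate p_B = 0.15, the upper bound in Section 9.6.
- Uncorrected chi-squared test, power target 80% (Section 9.6).
- Two-sided 0.05 (Section 9.5).

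**3. Formula**

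Let p̄ = (n_A·p_A + n_B·p_B)/(n_A + n_B), s0 = √[p̄(1−p̄)(1/n_A + 1/n_B)] and s1 = √[p_A(1−p_A)/n_A + p_B(1−p_B)/n_B]. Then power = Φ[(p_A − p_B − 1.96·s0)/s1].

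**4. How far the plan's own table reproduces**

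The smallest n_B giving 80% is 13 at X=7 (table 14), 7 at X=8 (table 14) and 33 at X=6 (table 30, power 78.9%). At X=9-10 fewer than 10 would do, so the stated minimum applies. At X=4 and X=5 no n_B up to 5,000 reaches 80% with Arm A fixed at 10; the maxima are 57.2% and 79.1%. The 4-6 row is therefore about right only for X=6.

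**5. Worked case, X=6**

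- n_B = 10: p̄ = 0.375, s0 = 0.2165, s1 = 0.1917. (0.45 − 1.96×0.2165)/0.1917 = 0.134, so power is 55.3%.
- n_B = 30: p̄ = 0.2625, s0 = 0.1607, s1 = 0.1681. (0.45 − 1.96×0.1607)/0.1681 = 0.804, so power is 78.9%.

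**6. All rows where the sections differ** (exact enumeration of the same test in brackets)

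| X | Power with 10 | Power with table number |
|---|---|---|
| 4 | 23.0% (19.7%) | 40.0% (39.3%) at 30 |
| 5 | 37.8% (34.9%) | 60.5% (60.9%) at 30 |
| 6 | 55.3% (53.5%) | 78.9% (79.6%) at 30 |
| 7 | 73.7% (72.5%) | 81.6% (80.5%) at 14 |
| 8 | 89.5% (87.9%) | 94.2% (93.3%) at 14 |

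**7. The same loss as a decision cut-off**

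This is the largest number of activated Arm B tumours that still gives a chi-squared of at least 3.841 in favour of Letrozole. At X=6 it is 1 of 10 (chi-squared 5.50; 2 of 10 gives 3.33) against 7 of 30 (4.60; 8 of 30 gives 3.66). At X=7 it is 2 of 10 against 4 of 14.

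**The case against.** The best defence is that Section 9.6 is the only place that derives an Arm B size, tabulates it and calls 10 a floor. Section 5.2 offers no derivation, calls its enrolment figure an estimate, and matches that floor. A careful reader could treat it as a baseline that the table overrides, and nothing suggests that staff would ignore the table. This bears on how likely the harm is. It does not remove the conflict, because the hedge in Section 5.2 applies to the number enrolled while the necessary evaluable number is stated flatly as 10.

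Three limits on the power figures stand:

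- **They sit at the 15% bound.** If the Arm B rate were assumed to be 10%, power with 10 patients would be 67% at X=6 and 84% at X=7; at an assumed 5%, 79.5% and 92%. The X=7 loss therefore matters only near the bound. The table's failure at X=5 also depends on it: at 5%, 30 patients give 87%.
- **They describe the binary sizing rule, not the planned analysis.** In Section 9.3, "An additional test will compare the magnitude of change in signal values in Arm A vs. Arm B", using an independent t-test.
- **They treat X/10 from ten tumours as the true rate,** as Section 9.6 does.

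The column label is a lesser matter, since Section 5.4 already replaces non-evaluable patients.

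**Conclusion.** The concern holds. The Arm B number in Section 5.2 contradicts Section 9.6 for every X from 4 to 8, and the plan does not resolve it. That conclusion rests on the text alone.

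The practical loss is narrower than the patient shortfall suggests. Measured against Section 9.6's 80% target at its 15% bound, aligning the sections restores roughly the intended power at X=6 (55% to 79%) and, to a smaller degree, at X=7 (74% to 82%). At X=8 little is lost. At X=4-5 alignment helps but does not reach 80%; the table's inadequacy there needs its own correction. The point should be fixed before Arm A is read out, because the size of a primary comparison should not be open to choice once those data are known.

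**What to change.** In Section 5.2, replace the fixed Arm B number with a reference to the rule, for example: *Arm B will enroll until Y evaluable patients are reached, Y being set from the Arm A result by the table in Section 9.6 (minimum 10); opening of Arm B is subject to the termination rule in Section 9.6.*

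In the Section 9.6 table, label the Y column as evaluable patients. This fits its stated purpose of supplying enough tumours and the replacement rule in Section 5.4.

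The cost is one sentence and one column header. The target itself does not rise above what Section 9.6 already sets. Enrolment may exceed Y where patients are non-evaluable, but those replacements are already required by Section 5.4.
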